4.3.6 Criteria to Resume Treatment with Study Drug

Subjects may resume treatment with study drug when the drug-related AE(s) resolve(s) to Grade 1 or baseline value. Subjects must be re-treated within 6 weeks from the previous dose. For selected patients who are assessed to be deriving clinical benefit from treatment or for patients where resumption of therapy is delayed, re-initiation of therapy may be delayed even further on a case-by-case basis in consultation with the Sponsor.

In the case of endocrine-related AEs, hormone replacement therapy may be utilized to restore physiologic function and to permit retreatment with nivolumab. If this is not possible, the subject must be discontinued from study therapy.

4.3.7 Criteria to Enter Extension Period

At the completion of two years of therapy, those subjects that meet the following criteria may continue to receive nivolumab at the dose of 3mg/kg every 2 weeks (14 days):

- Subject demonstrates investigator-assessed clinical benefit as defined by stable disease, partial response, or complete response
- Subjects who demonstrate a complete response can only receive treatment until confirmation of CR or for an additional 2 doses (whichever is longer) and then enter the follow up period.
- Subject is tolerating nivolumab therapy

All decisions to continue treatment in the Extension Period must be discussed with and approved by the BMS Medical Monitor and documented in the study records.

4.3.8 Treatment Beyond Progression of Disease

As described in [Section 1.1.9](#), accumulating evidence indicates a minority of subjects treated with immunotherapy may derive clinical benefit despite initial evidence of PD.⁷⁶

Subjects will be permitted to continue study drug beyond initial RECIST1.1 defined PD as long as they meet the following criteria:

- Continue to meet all other study protocol eligibility criteria
- Obtaining Investigator assessed clinical benefit and without rapid disease progression or clinical deterioration
- Stable performance status
- Tolerance of study drug
- Treatment beyond progression will not delay an imminent intervention to prevent serious complications of disease progression (eg, CNS metastases)

A follow up scan should be performed at the next assessment or earlier to determine whether there has been a decrease in the tumor size, or continued PD. The assessment of clinical benefit should be balanced by clinical judgment as to whether the subject is clinically deteriorating and unlikely to receive any benefit from continued treatment with study drug. If the investigator feels that the subject continues to achieve clinical benefit by continuing treatment, the subjects should remain on trial and continue to receive monitoring according to the Time and Events Schedule on Tables in [Section 5.1](#). The decision to continue treatment should be discussed with the BMS Medical Monitor and documented in the study records.

For the subjects who continue study therapy beyond progression, further progression is defined as an additional 10% increase in tumor burden volume from time of initial PD. This includes an increase in all target lesions and/or the development of new measurable lesions.

New lesions are considered measurable at the time of initial progression if the longest diameter is at least 10 mm (except for pathological lymph nodes, which must have a short axis of at least 15 mm). Any new lesion considered non-measurable at the time of initial progression may become measurable and therefore included in the tumor burden volume if the longest diameter increases to at least 10 mm (except for pathological lymph nodes, which must have a short axis of at least 15 mm).

For statistical analyses that include the investigator-assessed progression date subjects who continue treatment beyond initial investigator-assessed RECIST 1.1 defined progression will be considered to have investigator-assessed progressive disease at the time of the initial progression event.

4.3.9 Infusion Delays and Missed Doses

In the case that an infusion cannot be administered at a scheduled visit, it should be administered as soon as possible. If the delay is between 1 and 7 days, the procedures at the original scheduled

visit should be performed. If the delay is more than 7 days, the infusion at the original scheduled visit will be considered a missed dose, and the procedures at the next visit should be performed. Response assessments must never be omitted. Subsequent visits will follow accordingly from the actual date of last study drug administration. Subjects with infusion delays ≥ 8 weeks should normally discontinue treatment and enter the follow-up period with the exception of delays as described in [Section 4.3.6](#) and after specific consultation and agreement between the investigator and BMS Medical Monitor in settings where benefit/risk may justify continued study therapy.

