3 INVESTIGATIONAL PLAN

3.1 Study Design and Duration

Study Design: This is an exploratory, open-label, multicenter study of nivolumab and nivolumab in combination with ipilimumab.

Approximately 150 subjects with advanced melanoma (unresectable or metastatic) will be treated in this study in four (4) parts. Part 1 of this study will have two (2) cohorts consisting of approximately 40 patients each: cohort 1 will consist of anti-CTLA4 therapy-naïve patients and cohort 2 will consist of patients who have progressed on an anti-CTLA-4 regimen. Cohorts 1 and 2 will be administered nivolumab at 3 mg/kg dose level every 2 weeks. Subjects will go through a **screening period** of no longer than 28 days and eligible subjects will start the **treatment period** for a duration of 2 years depending on their response. Nivolumab will be administered by IV infusion every 14 days in 56 day cycles (on days 1, 15, 29 and 43 of each cycle). Response assessments will be performed on days 49-56. The response assessment must be completed before the first dose in the next cycle.

In Part 2, approximately 20 anti-CTLA4 therapy-naïve patients will be administered nivolumab at 1 mg/kg and ipilimumab at 3 mg/kg every 3 weeks for 4 doses, followed by nivolumab 3 mg/kg alone every 2 weeks (Arm A). This part of the study is aimed at defining the optimal window for on-treatment biopsy with concurrent nivolumab and ipilimumab therapy. All subjects will be required to undergo a pre-treatment biopsy and consent to on-treatment biopsy. Two (2) groups of approximately 10 patients each will be enrolled sequentially with the first group assigned to an on-treatment biopsy between Days 8 and 15 (weeks 2 and 3) after the start of therapy and the second group assigned to an on-treatment biopsy between Days 22 and 29 (subsequent to the second dose of therapy between weeks 4 and 5) after the start of therapy. Optimal biopsy timing will be defined as the biopsy window with the greatest pharmacodynamic

increase in intratumoral activated T cells compared to the pre-treatment biopsy. The defined optimal on-treatment biopsy window will be used in the third part of this study.

In Part 3, approximately 30 anti-CTLA4 therapy-naive patients will be randomized 2:1 and treated with one of the following:

- Arm A: nivolumab 1 mg/kg IV combined with ipilimumab 3 mg/kg IV Q3W for 4 doses then nivolumab 3 mg/kg IV Q2W
- Arm B: nivolumab 3 mg/kg IV Q2W

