4.1 Study Treatments

Treatment administration for nivolumab and ipilimumab (a ± 2 -day window will be allowed):

Table 4.1-1: Treatment Administration

Cohort/Arm	Dose	Infusion Time
1 and 2	3 mg/kg nivolumab every 2 weeks	60 minutes
A	1 mg/kg nivolumab + 3 mg/kg ipilimumab every 3 weeks x 4 doses and then 3 mg/kg nivolumab every 2 weeks	Part 2: nivolumab 60 minutes + 30 minutes break ipilimumab 90 minutes and then nivolumab 60 minutes
		Part 3: nivolumab 30 minutes + 30 minutes break ipilimumab 30 minutes and then nivolumab 30 minutes
B	3 mg/kg nivolumab every 2 weeks	30 minutes
D	1 mg/kg nivolumab + 3 mg/kg ipilimumab every 3 weeks x 4 doses and then 3 mg/kg nivolumab every 2 weeks	nivolumab 30 minutes + 30 minutes break ipilimumab 30 minutes and then nivolumab 30 minutes
E	3 mg/kg nivolumab every 2 weeks	30 minutes

Table 4.1-2: Product Description

Product Description and Dosage Form	Potency	Primary Packaging (Volume)/ Label Type	Secondary Packaging (Qty) /Label Type	Appearance	Storage Conditions (per label)
BMS-936558-01 Solution for Injection	100 mg (10mg/mL)	10 mL/ open label	10 vials per box/ open labels	Colorless to pale yellow, clear to opalescent solution; may contain particles	Store Refrigerated, 2-8° C (36-46 F) Protect from light and freezing.
Ipilimumab Solution for Injection	200 mg (5 mg/mL)	40 mL per vial/Open- label	4 vials per carton/Open-label	Clear, colorless to pale yellow liquid. May contain particles	2 to 8°C. Protect from light and freezing.

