4.3.4 Dose Delay Criteria

Study drug administration should be interrupted and increased monitoring of subjects should ensue if any of the following drug related adverse event(s) occurs:

- Any persistent grade ≥ 2 non laboratory non-skin drug related adverse event except for fatigue and weakness
- Any grade ≥ 2 endocrine drug-related adverse event
- Any grade ≥ 3 skin drug related adverse event

- Any Grade ≥ 3 drug-related laboratory abnormality (except lymphopenia, asymptomatic lipase or amylase increases, or any electrolyte abnormality without any clinical sequelae that is either spontaneously reversible or resolves with clinical management to grade 2 or less within 72 hours)
- ALT or AST $> 3X$ ULN (treatment may resume when the AE resolves to Grade 1)
- Patients with pre-existing neurologic or ophthalmologic anti-CTLA4 related adverse event who develop clinical symptoms leading to a 1 grade drug related shift (i.e. grade 1 to grade 2)
- Any AE, laboratory abnormality or inter-current illness which, in the judgment of the investigator, warrants skipping the dose of study medication

If dose delay is necessary, both nivolumab and ipilimumab must be delayed until treatment can resume. If a delay prevents subsequent infusion of ipilimumab, the dose of ipilimumab should be replaced as soon as possible. At least 19 days must elapse between the replacement dose of ipilimumab and the administration of the next dose of the combination.

The occurrence of clinically meaningful drug related AEs requires early recognition and prompt intervention. Management algorithms are available for suspected pulmonary, gastrointestinal, hepatic, renal, endocrine, neurological and skin toxicities. The recommendation is to follow the nivolumab IB adverse event algorithm. The algorithms can also be found on [Appendix 4](#).

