[Procedure Window ± 2 days]								
Procedure	Wk1 Day 1	Wk4 Day 1	Wk7 Day 1	Wk10 Day 1	Wk 13 Day 1 and every 2 weeks thereafter	End of Therapy	Follow- Up Visits 1 and 2^a	Notes
Pharmacokinetic Samples								
PK samples								See Table 5.5C or Table 5.5E for schedule of samples
Other Samples								
Immunogenicity blood sample (ADA)								See Table 5.5C or Table 5.5E for schedule of samples
Biomarker Samples								See Table 5.5B for schedule of samples
Efficacy Assessment								
Tumor Assessment			X		X			Subsequent assessments at week 23, then every 8 weeks thereafter. May be obtained up to 7 days prior to the required visit. CT Chest and CT or MRI abdomen, pelvis and all known sites of disease. Use same imaging method used at screening. Arm D only, MRI brain also (subjects in other arms who have stable brain metastases should have surveillance brain MRI approximately every 16 weeks and as clinically indicated).

Table 5.1D: On Treatment Procedural Outline (CA209038) - Part 2, Part 3 and Part 4: Arms A and D								
[Procedure Window ± 2 days]								
Procedure	Wk1 Day 1	Wk4 Day 1	Wk7 Day 1	Wk10 Day 1	Wk 13 Day 1 and every 2 weeks thereafter	End of Therapy	Follow- Up Visits 1 and 2^a	Notes
Survival Data Collection							X	Survival status should be continued every 3 months for the time remaining after the last office follow-up visit until 2 years from the first dose of study drug or until subject death, subject withdraws consent, subject is lost-to follow-up or the study is completed. This may be accomplished by visit or phone contact.
Clinical Drug Supplies								
IVRS drug vial assignment	X	X	X	X	X			
Nivolumab Infusion treatment	X	X	X	X	X			
Ipilimumab Infusion treatment	X	X	X	X				

^a Follow up Visit 1 and 2 will occur at 40-60 days and 101-120 days after the stop of study therapy, respectively. Efficacy is required at Follow up visit 2 only.

Table 5.1E: On Treatment Procedural Outline (CA209038) - Part 3 and Part 4: Arms B and E^a				
[Procedure Window ± 2 days]				
Procedure	Wk1 Day 1 and every 2 weeks thereafter	End of Therapy	Follow- Up Visits 1 and 2^b	Notes
Safety Assessments				
Targeted Physical Examination	X	X	X	To be performed only as clinically indicated
Vital Signs and Oxygen Saturation	X	X	X	Including BP, HR, temperature and oxygen saturation by pulse oximetry. Pulse oximetry at rest and after exertion within 72 hours prior to dosing
Physical Measurements (including performance status)	X	X	X	Weight and ECOG performance status

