Study Day	Time (Event)	Time (Relative to Start of Infusion) Hours:Min	SNP& HLA/ KIR typing	Tumor Ag specific T-cells with a CBC and differential	MDSCs	PB Gene Expression Profiling	PBMC Flow Cytometry with a CBC and differential	Soluble Factors (Serum)	Anti-Tumor Antibodies	PBMC Functional Assays with a CBC and differential	Tumor Biopsy
Week 3 Day 1	0 (predose)	00:00				X	X ^a	X		X ^a	
Week 4 Day 1	0 (predose)					X	X ^a	X		X ^a	X (+7 days after 2nd dose) ^{c,e}
Week 5 Day 1	0 (predose)	00:00		X ^a		X	X ^a	X		X ^a	
Week 7 Day 1	0 (predose)	00:00			X	X	X ^a	X	X	X ^a	
Week 13 Day 1	0 (predose)	00:00		X ^a			X ^a		X	X ^a	
Follow-up Visit 1 (40-60 days after last treatment)											X - obtain upon progression ^f
Follow-up Visit 2 (101-120 days after last treatment)											X - obtain upon progression ^f

Table 5.5B: CA209038 Pharmacodynamic and Biomarker Sampling Schedule (Parts 2, 3 and 4, Arms A, B, D and E)

Study Day	Time (Event)	Time (Relative to Start of Infusion) Hours:Min	SNP& HLA/ KIR typing	Tumor Ag specific T-cells with a CBC and differential	MDSCs	PB Gene Expression Profiling	PBMC Flow Cytometry with a CBC and differential	Soluble Factors (Serum)	Anti-Tumor Antibodies	PBMC Functional Assays with a CBC and differential	Tumor Biopsy
Upon occurrence of \geq Grade 3/4 drug-related AE								X			
Local surgery of isolated symptomatic lesions (see Section 3.4.1)											X ^f
Re-treatment after interrupted active treatment											X ^f

^a CBCs required will be done locally and not by central lab

^b Must contain sufficient tumor content (\geq 100 tumor cells in a 4 micron section) upon central pathology assessment;

^c Biopsy is strongly encouraged but not mandatory in Part 4

^d On-treatment biopsy window for Part 2, group 1 biopsy is Week 2, Day 1+7 days; potential on-treatment biopsy window for Parts 3 and 4, if determined to be optimal biopsy window.

^e On-treatment biopsy window for Part 2, group 2 is Week 4, Day 1+7 days; potential on-treatment biopsy window for Parts 3 and 4, if determined to be optimal biopsy window.

^f Biopsy is strongly encouraged but not mandatory. May be done at either Follow-up visit 1 or Follow-up visit 2

Table 5.5C: PK and ADA Sampling Schedule - Part 2 Arm A

Study Day	Time (Event)	Time (Relative to Start of Nivolumab Infusion) Hours Min ^a	PK Serum Sample Nivolumab	Immuogenicity Sample Nivolumab	PK Serum Sample Ipilimumab	Immunogenicity Sample Ipilimumab
Week 1 Day 1	0 (predose)	00:00	X	X	X	X

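### After an adverse-event hold of more than 7 days in the combination phase, Protocol 4.3.9 and 4.3.4 leave open whether three or four ipilimumab doses are given; separately, SAP 7.2.3 can count a one-dose biopsy as second-window data

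*Protocol*

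**What the plan says.** **Regimen.** Protocol Table 4.1-1 gives Arms A and D "1 mg/kg nivolumab + 3 mg/kg ipilimumab every 3 weeks x 4 doses and then 3 mg/kg nivolumab every 2 weeks". In Table 5.1D the row "Ipilimumab Infusion treatment" is marked at Weeks 1, 4, 7 and 10 only. From Week 13 the schedule has nivolumab alone.

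**Late infusions, Protocol 4.3.9.** The section opens: "In the case that an infusion cannot be administered at a scheduled visit, it should be administered as soon as possible". It then separates short from long delays: "If the delay is more than 7 days, the infusion at the original scheduled visit will be considered a missed dose". After a long delay the subject goes on to whatever the following visit calls for. Later visits are timed from the last actual administration. The only exception it names is in Section 4.3.6.

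**Adverse-event holds, Protocol 4.3.4.** Both drugs are held together. Then: "If a delay prevents subsequent infusion of ipilimumab, the dose of ipilimumab should be replaced as soon as possible". At least 19 days must pass between that replacement and the next combination dose. No limit on the length of the delay is given here, and making up nivolumab is not mentioned.

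**Limit on holds, Protocol 4.3.6.** Re-treatment must come within 6 weeks of the previous dose unless the sponsor is consulted.

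**Biopsy window.** Protocol 3.1 describes the second Part 2 group (Days 22-29) as "subsequent to the second dose of therapy between weeks 4 and 5", and Table 5.5B labels the same biopsy "X (+7 days after 2nd dose". SAP 7.2.3 assigns Part 2 biopsies to windows by the day counted from the start of therapy and drops those outside both windows from the comparison.

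**The concern.** For an adverse-event hold of more than 7 days in the combination phase, both sections apply and they point to different next steps. One moves the subject past the held visit; the other calls for the ipilimumab to be given again. Sites could therefore deliver different ipilimumab totals, and start nivolumab 3 mg/kg at different times, under one arm label and after the same event. Exposure and dose-intensity summaries would mix the two.

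A second matter concerns the primary pharmacodynamic work. Part 2 exists to choose the biopsy window for Part 3, and the later window is meant to show the effect of two doses. Classifying a biopsy by calendar day alone does not ensure that two doses were given.

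**Working it through.** **Planned schedule.** Four doses 21 days apart fall on Days 1, 22, 43 and 64 (Weeks 1, 4, 7 and 10). The phase lasts 4 × 21 = 84 days, so Week 13 Day 1 is Day 85. This agrees with Tables 4.1-1 and 5.1D and with the 4 cycles and 84 days in the SAP 7.4.1 nivolumab formula.

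**Where both rules apply.** Section 4.3.9 needs a delay of at least 8 days. Six weeks from the previous dose is 42 days, and 42 − 21 = 21 days of delay. The overlap without sponsor consultation is therefore a delay of 8 to 21 days.

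**Dose counts for one 14-day hold.** I assume 21-day spacing from the actual dose date. *Missed* takes 4.3.9 literally, so the resumed visit is the next one on the schedule. *Replaced* follows 4.3.4, and later visits shift. The SAP relative dose intensity (RDI) for ipilimumab is cumulative dose / [3 × (last − first + 21)/21] × 100.

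| Held dose | Missed: ipilimumab days | Total, RDI | Replaced: ipilimumab days | Total, RDI |
|---|---|---|---|---|
| none (plan) | 1, 22, 43, 64 | 12 mg/kg, 100% | – | – |
| Week 4 | 1, 36, 57 | 9 mg/kg, 9/11 = 82% | 1, 36, 57, 78 | 12 mg/kg, 12/14 = 86% |
| Week 7 | 1, 22, 57 | 9 mg/kg, 82% | 1, 22, 57, 78 | 12 mg/kg, 86% |
| Week 10 | 1, 22, 43 | 9 mg/kg, 9/9 = 100% | 1, 22, 43, 78 | 12 mg/kg, 86% |

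For holds of 8 to 20 days at Week 4 or 7, RDI runs from 89% down to 76% if missed and from 91% down to 81% if replaced. At Week 10 it stays at 100% if missed.

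Three points follow.

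- The difference is one ipilimumab dose: 3 × 3 = 9 against 4 × 3 = 12 mg/kg, or 25% less. Nivolumab monotherapy starts on Day 78 if missed and Day 99 if replaced.
- For a held Week 10 dose, 4.3.9 leads to Week 13 procedures, where Table 5.1D has no ipilimumab. A replacement has no scheduled visit, and the lost dose does not show in RDI.
- Combination-phase nivolumab totals 3 mg/kg if missed, and 3 or 4 mg/kg under 4.3.4, which is silent on it. The SAP denominator assumes four cycles in 84 days. Reading its last dose date as days since first dose, the first monotherapy dose at 84 days gives 7/[4 + 3 × 14/14] = 7/7 = 100% as planned. Three combination doses with the same timing give 6/7 = 86%.

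**Subjects.** Part 2 has about 20, Part 3 Arm A about 20 (two thirds of 30) and Arm D about 10: 20 + 20 + 10 = 50 planned.

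**Biopsy.** The second dose is due on Day 22. Held more than 7 days, it falls on Day 22 + 8 = 30 or later under either rule. A Days 22-29 biopsy then follows one dose, but its day fits the second window, so SAP 7.2.3 leaves it there. A biopsy that waits for the delayed dose falls on Day 30 or later and is excluded as outside both windows. In a group of about 10, one such subject is 1/10 = 10% of the data.

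**The case against.** The best reply is that the two sections can be read together. Section 4.3.9 begins by asking for a late infusion to be given promptly and never bars making up a missed dose. Its missed label may only decide which visit's procedures apply, while 4.3.4, as the specific rule for adverse-event holds, governs the ipilimumab. This stands to the extent that the text is an unresolved ambiguity and not an outright contradiction. It does not settle the count: when treatment resumes, the next visit already includes ipilimumab after a held Week 4 or 7 dose, and the documents do not say whether that infusion is the replacement or the next scheduled dose. After a held Week 10 dose there is no ipilimumab visit left.

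The regimen text also defines the combination phase by dose count, which favours four. That is fair, but 4.3.9 makes no exception for it.

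SAP 7.4.1 and 7.4.2 report number of doses, cumulative dose, delays and omissions. Unequal exposure would therefore be visible there, though not in RDI after a missed Week 10 dose.

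Section 4.3.5 requires stopping for most Grade 3 or higher non-laboratory drug-related events, so many serious cases never reach the overlap. This limits the number affected but does not remove the gap.

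Finally, Table 5.5B ties the later biopsy to the second dose. That supports the intended meaning of the window, but SAP 7.2.3 does not carry the condition over.

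**Conclusion.** The point holds in a limited form. For adverse-event holds of about 8 to 21 days in Arms A and D, the protocol allows three or four ipilimumab doses (9 or 12 mg/kg) after the same event and does not say whether nivolumab 1 mg/kg is also made up. The day counts assume 21-day spacing from the actual dose date. No sample size or power figure is affected.

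A reader might infer more than the documents support:

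- *Replacement is mandatory, or a full fourth combination dose is prescribed.* Section 4.3.4 uses should, names ipilimumab only, and distinguishes the replacement from the next combination dose.
- *Every long delay is caught.* Delays outside 4.3.4, such as logistic ones, fall under 4.3.9 alone.
- *Fifty subjects are affected.* That is the planned enrolment of the combination arms. The documents give no delay rate, so the affected number is unknown.
- *The dosing ambiguity causes the biopsy problem.* It does not. The misclassification follows from any Week 4 delay of more than 7 days under either rule, and reconciling the dosing sections alone would leave it in place.

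The biopsy point stands separately: Protocol 3.1 and Table 5.5B define the later window as after the second dose, while SAP 7.2.3 classifies by day alone.

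**What to change.** 1. Reconcile Protocol 4.3.4 and 4.3.9 for the combination phase of Arms A and D, with a cross-reference. State what happens to a combination dose held more than 7 days, whether any make-up covers ipilimumab alone or both drugs, which visit comes next, and when the switch to nivolumab monotherapy occurs. The sponsor decides which dosing rule holds.
2. Align the result with the four-dose regimen in Table 4.1-1, the visits in Table 5.1D (including a held Week 10 dose), and the 4-cycle, 84-day term in the SAP 7.4.1 nivolumab dose-intensity formula.
3. In SAP 7.2.3, count a biopsy in the Days 22-29 group only if the second dose was given before it.

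The cost is amendment wording, a small change to SAP 7.4.1 and one line in SAP 7.2.3. Possibly one or two biopsies would leave the window comparison; that number is a guess in the absence of a delay rate.
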